The safety results from the dose escalation part of the first-in-human study 15051 in 45 patients with advanced cancer (BAY 94-9343 dose range, 0.15-7.5 mg/kg q3w) were as follows: 1) The non-tolerable dose of BAY 94-9343 was 7.5 mg/kg q3w; the non-tolerable toxicities at 7.5 mg/kg q3w were corneal toxicity (blurry vision and keratitis due to corneal epitheliopathy), peripheral neuropathy and increase in serum amylase and lipase; 2) The maximum tolerated dose was 6.5 mg/kg q3w; the only dose-limiting toxicity observed at this dose level was the asymptomatic Grade 3 increase in serum AST/ALT; 3) The most common treatment-emergent adverse events at least possibly related to BAY 94-9343 were fatigue, nausea, vomiting, anorexia, peripheral neuropathy, myalgia, weakness and diarrhea. The most common treatment-emergent lab abnormalities were lymphopenia, hypoalbuminemia, hyponatremia, hyperglycemia and hypokalemia; 4) at doses below the non-tolerated dose, the TEAEs were mostly mild and not clinically significant except for cardiac chest pain, hypertension, grade 3 increase in ALT and AST, and decrease in platelets and sodium.

The safety results from the MTD Expansion 6.5 mg/kg q3w cohort, which evaluated the MTD for BAY 94-9343 determined in the dose escalation cohorts were as follows: 1) BAY 94-9343 at 6.5 mg/kg given IV once every 3 weeks was considered tolerable in the two cohorts of subjects with ovarian cancer (n=20) and pleural or peritoneal mesothelioma (n=12); 2) Overall, 16 of 32 (50%) subjects treated at 6.5 mg/kg q3w have required dose reduction to 5.5 mg/kg q3w and 4 (25%) of these subjects required another dose reduction to 4.5 mg/kg; 3) the safety finding of particular relevance was the high incidence of corneal toxicity (blurred vision and keratitis with vision impairment due to corneal epithelial microcysts or deposits in 12 of 32 subjects) causally attributed to BAY 94-9343; 4) although being fully reversible in the vast majority of cases, the corneal toxicity invariably necessitated lengthy treatment interruption and dose reduction; 5) otherwise the safety profile of BAY 94-9343 in the MTD

Expansion 6.5 mg/kg q3w cohort was very similar to that observed in dose escalation cohorts up to and including the Cohort 9 (6.5 mg/kg q3w), with mostly mild TEAEs and remarkably low incidence of drug-related SAEs. One patient in a Japanese cohort with pancreatic cancer developed drug-induced liver injury.

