- c Febrile neutropenia is defined as ANC < 1000/mm³ and fever (a single body temperature reading of > 38.3°C [101°F] or a sustained body temperature of ≥ 38°C [100.4°F] for more than 1 hour).

Clinical Study Protocol

19-September-2018

BAY 94-9343 (Anetumab in Pancreatic Cancer)
Version 4.0

Page: 28 of 77

Table 2-4: Dose adjustments in response to pre-infusion values

Absolute neutrophil count (/mm ³)	Platelets (/mm ³)	Hemoglobin (g/dL)	Treat	Anetumab ravtansine dose adjustment
≥ 1,000	and	≥ 75,000	Treat on time	Adjust dose by nadir ^a counts in previous cycle per investigator's discretion
< 1,000	and	< 75,000	Delay until ANC ≥ 1.0 and platelets ≥ 75,000 ^b	Decrease by 1 dose level ^c
		< 8	Delay until Hb ≥ 8 ^b	Re-start at the same dose or decrease by 1 dose level ^c (at investigator's discretion)

ANC = Absolute neutrophil count; C = Cycle; CBC = Complete blood count; D = Day; Hb = Hemoglobin; Q3W = Every 3 weeks; TEAE = Treatment-emergent adverse event

- a Site visits and blood test for CBC (and biochemistry) on D8 and D15 will be performed on C1, C2 and C3 only. From Cycle 4 onwards, visits and procedures on D8 and D15 are no longer required.
- b Treatment will be discontinued if the TEAE fails to resolve to Grade ≤ 1 (or Hb ≥ 9 g/dL in case of anemia) within 6 weeks after the last dose of anetumab ravtansine.
- c Dose reduction by 1 dose level translates to a change from 6.5 mg/kg Q3W to 5.5 mg/kg Q3W, or from 5.5 mg/kg Q3W to 4.5 mg/kg Q3W. Not more than 2 dose reductions from the starting dose level are permitted.

7.3.2.2 Non-hematological toxicities**Non-hematological toxicities requiring dose or infusion modification**

- CTCAE Grade 2 or Grade 3 anetumab ravtansine infusion reaction or other CTCAE Grade 2 or Grade 3 hypersensitivity events (see Section 7.3.2.1.3)
- AST and/or ALT increase > 5.0 x ULN (CTCAE Grade ≥ 3)
- AST and/or ALT increase > 3.0 x ULN (CTCAE Grade ≥ 2) with concomitant increase in total bilirubin > 1.5 x ULN (CTCAE Grade ≥ 2)
- Total bilirubin > 3.0 x ULN (CTCAE Grade ≥ 3)
- Bayer Grade ≥ 3 corneal toxicity (see below and **Table 2-6**)
- Any other Grade ≥ 3 non-hematological toxicity that, in the investigator's opinion, warrants treatment modification (see **Table 2-5**), **excluding** the following:
 - Nausea, vomiting, or diarrhea if manageable with anti-emetics or antidiarrheals within 7 days
 - Hair loss
 - Fatigue lasting ≤ 72 h

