 - Certain asymptomatic laboratory assessments without a clear clinical correlate, if the investigator determines that this TEAE would not require treatment modification
- Any other toxicity irrespective of the type or severity that represents a clinically significant risk to patient in the investigator's opinion.

Dose modifications for non-hematological toxicity

If treatment modification is required due to a **non-hematological TEAE** as listed above, other than corneal toxicity and infusion reaction/hypersensitivity events, and the continuation of treatment is appropriate, the anetumab ravtansine dose will be either reduced or maintained as is at investigator's discretion (see **Table 2-5**).

Table 2-5: Dose adjustments in response to non-hematologic toxicities

CTCAE v4.03 grade	Anetumab ravtansine dose delay / interruption	Anetumab ravtansine dose modification
Grade 1 – 2 ^a	Treat on time	No change required (at investigator's discretion)
Grade 3	1 st appearance: Delay/Interruption until Grade ≤ 2 ^b	Re-start at the same dose or decrease by 1 dose level ^c (at investigator's discretion)
	2 nd appearance: Delay/Interruption until Grade ≤ 2 ^b	Decrease by 1 more dose level ^c
	3 rd appearance: Permanently discontinue	
Grade 4	Permanently discontinue	

ALT = Alanine aminotransferase; AST = Aspartate aminotransferase; CTCAE = Common Terminology Criteria for Adverse Events; Q3W = Every 3 weeks; TEAE = Treatment-emergent adverse event

- a AST and/or ALT increase of CTCAE Grade 2 with concomitant increase in total bilirubin of CTCAE Grade 2 will be treated as a CTCAE Grade 3 event.
- b Treatment will be discontinued if the TEAE fails to resolve to Grade \leq 1 within 6 weeks after the last dose of anetumab ravtansine.
- c Dose reduction by 1 dose level translates to a change from 6.5 mg/kg Q3W to 5.5 mg/kg Q3W, or from 5.5 mg/kg Q3W to 4.5 mg/kg Q3W. Not more than 2 dose reductions from the starting dose level are permitted.

The anetumab ravtansine dose reduction due to non-hematological TEAE will be done as described below:

- If the patient experienced a TEAE requiring dose reduction at the 6.5 mg/kg Q3W dose level, the subsequent anetumab ravtansine dose should be reduced to 5.5 mg/kg Q3W.
- If the patient experienced a TEAE requiring dose reduction at the 5.5 mg/kg Q3W dose level, the subsequent anetumab ravtansine dose should be reduced to 4.5 mg/kg Q3W.

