7.3.2.4 Continuation of treatment with anetumab ravtansine

Treatment with anetumab ravtansine could be re-started at the appropriate dose if the TEAE requiring dose modification has resolved to Grade < 2 within 6 weeks after the last dose of anetumab ravtansine.

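### For a combined Grade 2 transaminase and Grade 2 bilirubin rise, Table 2-5 does not say whose grade ends the hold, and its release level conflicts with Section 7.3.2.4

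*Combined protocol and SAP*

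**What the plan says.** Section 7.3.2.2 lists three liver findings that call for dose or infusion modification: transaminases above 5.0 x ULN, bilirubin above 3.0 x ULN, and a combination, given as "AST and/or ALT increase > 3.0 x ULN (CTCAE Grade ≥ 2) with concomitant increase in total bilirubin > 1.5 x ULN" with bilirubin also labelled Grade ≥ 2.

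Table 2-5 in the same section sets the action by grade. The Grade 1–2 row treats on time. Note a takes one case out of that row: "AST and/or ALT increase of CTCAE Grade 2 with concomitant increase in total bilirubin of CTCAE Grade 2 will be treated as" a Grade 3 event. The Grade 3 row says, at first and second appearance, "Delay/Interruption until Grade ≤ 2". At first appearance the investigator may re-start at the same dose or one level lower. A second appearance brings a dose decrease and a third a permanent stop. Note b, attached to the same cells, adds "Treatment will be discontinued if the TEAE fails to resolve to Grade" ≤ 1 within 6 weeks after the last dose. The withdrawal criteria in Section 6.3.2 (text of Figure 2-1) repeat that limit.

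Section 7.3.2.4 gives a general rule. Treatment may be re-started "if the TEAE requiring dose modification has resolved to Grade < 2 within 6 weeks after the last dose of anetumab ravtansine".

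**The concern.** Note a assigns a higher grade to a pair of Grade 2 findings, and the row it points to releases at Grade ≤ 2. If release is judged on each component, the condition for ending the delay is already true when the event begins. Section 7.3.2.4 would not release the same patient. Two sites could each follow the protocol and act differently on one liver event.

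The protocol gives reason to care about the liver. Section 3.1 reports that "One patient in a Japanese cohort with pancreatic cancer developed drug-induced liver injury" and that a Grade 3 AST/ALT increase was the only dose-limiting toxicity at 6.5 mg/kg. Inclusion criterion 8 (Section 6.1.2) admits patients with liver involvement at ALT/AST up to 5 x ULN, and Section 7.3.2.2 labels values above 3.0 x ULN as Grade 2 or higher. Such a patient needs only a bilirubin above 1.5 x ULN to reach the combined thresholds. Whether a transaminase level already raised at entry counts as an increase is not stated.

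There is also a reporting consequence. Toxicity is a secondary objective, and Section 10.2.2.2 tabulates patients with dose interruption, reduction or discontinuation due to an AE. Which rule a site follows determines whether a patient enters those counts. With at most 30 patients, one patient is 1/30 = 3.3 percentage points.

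**Working it through.** The plan gives no figure on this point to reproduce, so the check is one of logic on its own cut-offs.

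**Inputs (Section 7.3.2.2).** ALT/AST: above 3.0 x ULN is Grade 2, above 5.0 x ULN is Grade ≥ 3. Bilirubin: above 1.5 x ULN is Grade 2, above 3.0 x ULN is Grade ≥ 3. Lower values are shown as ≤ 1. The laboratory values below are illustrative, one for each grade band.

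**Release rules compared.**
- A: Table 2-5, Grade ≤ 2 read on each component, so max(ALT/AST grade, bilirubin grade) ≤ 2.
- B: Table 2-5, Grade ≤ 2 read on the assigned grade, which is 3 while both components are Grade ≥ 2 and otherwise the higher of the two.
- C: Section 7.3.2.4, so max(ALT/AST grade, bilirubin grade) < 2.

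| ALT/AST x ULN | Bilirubin x ULN | Grades | Listed trigger | A met | B met | C met |
|---|---|---|---|---|---|---|
| 2.5 | 1.2 | ≤1 / ≤1 | no | yes | yes | yes |
| 2.5 | 2.0 | ≤1 / 2 | no | yes | yes | no |
| 2.5 | 3.5 | ≤1 / ≥3 | yes | no | no | no |
| 4 | 1.2 | 2 / ≤1 | no | yes | yes | no |
| 4 | 2.0 | 2 / 2 | yes | yes | no | no |
| 4 | 3.5 | 2 / ≥3 | yes | no | no | no |
| 6 | 1.2 | ≥3 / ≤1 | yes | no | no | no |
| 6 | 2.0 | ≥3 / 2 | yes | no | no | no |
| 6 | 3.5 | ≥3 / ≥3 | yes | no | no | no |

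**At onset.** Six cells are listed triggers. In the five with a Grade ≥ 3 component, no rule is met, so drug is held whichever is used. In the 2 / 2 cell, A is met at once, while B and C are not.

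**During recovery.** Suppose a 2 / 2 event improves until one component is below Grade 2 (rows 2.5 / 2.0 and 4 / 1.2). A and B both release and C does not. So neither reading of Table 2-5 agrees with Section 7.3.2.4.

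**Against the 6-week rule.** Note b and Section 6.3.2 require Grade ≤ 1 within 6 weeks of the last dose. A and B both allow re-dosing with a component still at Grade 2. Because the clock runs from the last dose, a re-dose can be read as restarting it. The text does not settle this.

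**Trigger against note a.** The list in Section 7.3.2.2 names Grade ≥ 2 with Grade ≥ 2, but note a names only Grade 2 with Grade 2. A component at Grade 3 puts the event in the Grade 3 row by its own grade, so entry is unaffected. Release is less clear. If an event that began at Grade 3 with Grade 2 improves to 2 / 2, A releases it. B holds it only if note a is taken to apply again at that moment.

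**The case against.** A reader might infer that the protocol's liver-injury hold holds nothing, or that every first combined event carries a required delay of zero days and no dose change. The documents do not support that, for four reasons.

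- Note a says the pair is to be handled as Grade 3. If the assigned grade governs entry to the row, it can equally govern release, and then the hold is real until the pair breaks up. Using the assigned grade for entry and the component grades for release is one reading, not the only one.
- Section 7.3.2.4 applies to any TEAE requiring dose modification, and the combined event is on that list. Read with it, re-start at Grade 2 is barred.
- Note b, the withdrawal criteria and the steps at second and third appearance still act on the event. Section 6.3.2 also requires withdrawal when the investigator judges that continuing would be harmful.
- The background evidence does not show the event in question. The dose-limiting toxicity was a Grade 3 AST/ALT increase, which Table 2-5 does hold. No grade, bilirubin value or dose is given for the one drug-induced liver injury.

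All four stand as limits on the size of the point. They do not remove it. The assigned-grade reading is nowhere written, and it still releases earlier than Section 7.3.2.4. A stricter rule in another section does not cure a looser one in the table, because the document does not say which takes precedence. Discretion to re-start at the same dose applies to every first Grade 3 non-hematologic event and is not a fault particular to the liver rule.

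**Conclusion.** The point holds as an ambiguity within Table 2-5 and a contradiction between Table 2-5 and Section 7.3.2.4. The empty hold at onset arises in one of the six triggering grade combinations, and only if release is read by component. That is a count of table cells, not of patients, and no event rate can be derived. The conflict over when drug may be re-started arises on both readings of Table 2-5.

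This rests on three assumptions: the grade cut-offs are those printed in Section 7.3.2.2; a component still at Grade 2 does not satisfy Grade < 2 in Section 7.3.2.4; and the event is at least possibly drug-related, as Section 7.3.2 requires. That results would in fact differ by site is a possibility the text leaves open, not something the documents show. The two-stage design, its error rate and its power are unaffected. The point still warrants correction because it concerns re-dosing during a liver event and the text cannot be followed consistently.

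**What to change.** The sponsor's clinical team should reconcile the trigger list in Section 7.3.2.2, the Grade 3 row of Table 2-5 with its notes a and b, Section 7.3.2.4, and the 6-week criterion in Section 6.3.2. The result should be one re-start condition for the combined liver event, stated the same way in each place. The text should say whether the condition applies to each component or to the pair, and whether note a covers Grade 2 with Grade 2 only or Grade ≥ 2 with Grade ≥ 2. It should also say whether the 6-week clock restarts after a re-dose. Which level is right is a clinical decision on which this review takes no position.

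Section 7.3.2.5 sends the reader to 6.3.1.2 for withdrawal criteria, but that section covers full screening failure and the criteria stand in 6.3.2. The cross-reference can be corrected at the same time.

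The cost is a short amendment or clarification letter and a notice to the sites. Sample size, stopping rule and data collection do not change. If patients have already been treated, any combined Grade 2 events should be listed with the re-start rule that was applied, so that the interruption and reduction counts can be interpreted.

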7.3.2.3 Miscellaneous toxicities

IV infusion reaction and other hypersensitivity events

If a patient experiences a CTCAE Grade 2 or Grade 3 anetumab ravtansine infusion reaction or other CTCAE Grade 2 or Grade 3 hypersensitivity event deemed at least possibly related to anetumab ravtansine, the infusion of anetumab ravtansine will be interrupted.

If treatment interruption is caused by a CTCAE Grade 2 or Grade 3 anetumab ravtansine infusion reaction or other CTCAE Grade 2 or Grade 3 hypersensitivity event deemed at least possibly related to anetumab ravtansine, treatment may be re-started at the time determined at the investigator's discretion. Re-treatment should be at the infusion rate reduced by 50%, along with anti-allergic prophylaxis (e.g. anti-histamines, acetaminophen, and/or corticosteroids) chosen at the investigator's discretion or according to the institutional guidelines.

Miscellaneous toxicities requiring dose modification

For any toxicity \leq Grade 2 assessed as related to anetumab ravtansine by the investigator, dose modification should be considered. Such toxicities might be \leq Grade 2 toxicities which interfere with the activities of daily life, such as long lasting fatigue, or anorexia, or corneal toxicity with vision impairment etc. A dose change might be necessary in order to ensure the patient's compliance. These toxicities may be declared "TEAE requiring treatment modification" after consultation between the investigator and the sponsor.

Dose modifications for corneal toxicity

For the TEAE of corneal morphology changes and the best corrected visual acuity (BCVA) changes (blurred vision), the Bayer severity grading system (see **Table 2-6** and **Table 2-7**) will be used to assess the severity of TEAEs requiring modification of anetumab ravtansine treatment.

TEAE of corneal morphology changes deemed to be at least possibly related to anetumab ravtansine would require modification of anetumab ravtansine treatment (dose reduction or permanent discontinuation of treatment) according to the following principles (see **Table 2-6**).

Clinical Study Protocol

18-December-2017

BAY 94-9343 (Anetumab in Pancreatic Cancer)
Version 2.0

Page: 32 of 77

Table 2-6: Bayer classification and management of corneal epitheliopathies

	Grade 0	Grade 1	Grade 2	Grade 3	Grade 4
Corneal Morphology	No pathologic changes	Any stage of superficial punctate keratitis ^a	Epithelial opacities Micro-Cysts Micro-deposits Corneal erosion Corneal erosion Stromal opacity: non-central	Corneal ulcer without risk of acute rupture Stromal opacity: central	Corneal ulcer more severe than Grade 3
	Grade 0	Grade 1	Grade 2	Grade 3	Grade 4
Eye Treatment ^b	Ocular lubricants at the discretion of investigator, in consult with ophthalmologist	Ocular lubricants; add topical steroids if superficial punctate keratitis shows treatment-emergent progression by ≥ 2 SPK Grades	Intensive Treatment with ocular lubricants enhanced with ointments; topical steroids; therapeutic contact lens may be considered at the discretion of investigator in consult with ophthalmologist	Intensive therapy with ointments; topical steroids; therapeutic contact lens or occlusion recommended at the discretion of investigator in consult with ophthalmologist	Intensive therapy with lubricants, ointments, topical steroids and antibiotics as needed; occlusion or therapeutic contact lens recommended; amniotic membrane transplant and other locally approved therapies to be considered at the discretion of investigator in consult with ophthalmologist

Clinical Study Protocol

18-December-2017

BAY 94-9343 (Anetumab in Pancreatic Cancer)
Version 2.0

Page: 33 of 77

	Grade 0	Grade 1	Grade 2	Grade 3	Grade 4
Anetumab ravnansine^c	No change	No change	Keep treatment dose level and schedule if the ophthalmological exam can be performed as needed; otherwise consider dose reduction by -1 dose level without dose schedule change at the discretion of investigator in consult with ophthalmologist	1) Decrease dose to -1 dose level (or -2 dose level if event does not resolve to Grade ≤ 2 at the -1 dose level within 3 weeks) 2) Re-start at the original dose level if the first Grade 3 event resolves to Grade ≤ 2 within 3 weeks and does not recur 3) If not resolved within 3 weeks continue at reduced -2 dose level (or -3 dose level)	Discontinue treatment

SPK = Superficial punctate keratitis a Oxford Schema must be used for grading SPK from stage 0 to VI.

- b Other remedial therapies for corneal epitheliopathy may be added or substituted at investigator's discretion or according to the institutional standards.
- c Treatment decisions are based on corneal morphology changes only, not on visual acuity changes.

Clinical Study Protocol

18-December-2017

BAY 94-9343 (Anetumab in Pancreatic Cancer)
Version 2.0

Page: 34 of 77

Table 2-7: Bayer classification of visual acuity changes

	Grade 0	Grade 1	Grade 2	Grade 3	Grade 4
Visual acuity	No findings, no reporting from the patient	Symptomatic visual acuity loss < 3 lines (ETDRS Equivalent ^a)	Visual acuity loss \geq 3 lines, but < 6 lines (ETDRS equivalent ^a)	Visual acuity loss \geq 6 lines (ETDRS equivalent ^a)	Visual acuity loss \geq 6 lines (ETDRS equivalent ^a) leading to blindness

ETDRS = Early Treatment Diabetic Retinopathy Study

^a In the ETDRS chart, each loss of 3 lines corresponds to halving the visual acuity. In other charts, an equivalent amount of visual acuity loss must be reached in order to meet this threshold.

Recommended measures in case of eye dryness and ocular hypertension

Changes in tear production as evaluated by the Schirmer test and in intraocular pressure (IOP) are not expected to occur as a direct consequence of anetumab ravtansine therapy. However, IOP may increase in some patients as a consequence of the therapy with topical steroid eyedrops. Since these drugs may be required to manage the corneal epitheliopathy syndrome, IOP will be monitored during this study for patients receiving topical steroid eyedrops.

Changes in IOP should be managed by the investigator following exam by an ophthalmologist. The remedial therapy should be chosen at investigator's discretion or according to the institutional standards; therapeutic measures can include modification of the type or posology of topical steroid eye drop, initiation of topical IOP lowering drugs and any other therapeutic options according to the local SoC. Ophthalmological monitoring should be maintained until the IOP has returned to normal values.

Reductions in tear production evaluated by the Schirmer test, while not being a part of the corneal epitheliopathy syndrome, are a risk factor for developing ocular surface disease including corneal epithelial defects. Therefore, the tear production will be evaluated in this study to determine if changes in this parameter may be helpful to identify patients at higher risk of developing the corneal epitheliopathy syndrome. Abnormal values in the Schirmer test should be evaluated and managed by the investigator following exam by an ophthalmologist to provide adequate protection to the corneal epithelium. The remedial therapy for the treatment-emergent changes in the Schirmer's test (dry eye) should be chosen at investigator's discretion or according to the institutional standards. These measures may include topical lubricants such as eye drops and ointments, punctual occlusion, use of therapeutic contact lenses and any other treatment approaches according to the local SoC.

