- Patient starts treatment with any other anti-cancer therapy or any other prohibited medication as per Section 8.1.
- Positive serum β -HCG test consistent with pregnancy. Pregnancy should be reported along the same timelines as an SAE.
- Use of illicit drugs or other substances that may, in the opinion of the investigator or his designated associate(s), have a reasonable chance of contributing to toxicity or otherwise confound the results.
- Development of any intercurrent illness or situation which may, in the judgment of the investigator, affect assessments of clinical status and study endpoints to a relevant degree.
- Lost to follow-up.
- Death.

Patients must be withdrawn from **treatment with anetumab ravtansine** if any of the following occurs:

- CTCAE Grade 4 non-hematological AE and Bayer Grade 4 corneal toxicity (see Table 2-6) (except at the investigator's discretion in case of certain Grade 4 abnormality of laboratory assessments, such as abnormal laboratory assessments without corresponding clinical symptoms, or abnormal laboratory assessments that can be easily clinically managed).
- If any type of TEAE requiring dose modification does not resolve to Grade ≤ 1 (or Hb ≥ 8 g/dL in case of anemia) within 6 weeks after the last dose of anetumab ravtansine.
- Delay in anetumab ravtansine administration of 3 weeks (max. 6 weeks between 2 infusions of study drug).
- TEAE requiring dose reduction when already at the 4.5 mg/kg Q3W dose level (minimum dose).
- More than 2 dose reductions required due to a TEAE.

AE = Adverse event; β -HCG = β subunit of human chorionic gonadotropin; CTCAE = Common Terminology Criteria for Adverse Events; Hb = Hemoglobin; RECIST = Response Evaluation Criteria in Solid Tumors; PD = Progressive disease; Q3W = Every 3 weeks; SAE = Serious adverse event; TEAE = Treatment-emergent adverse event

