7.3.2.1 Hematological toxicities

Dose modifications for hematological toxicity

- If treatment modification is required due to a hematological TEAE, and the continuation of treatment is appropriate, the anetumab ravtansine dose will be adjusted as described in **Table 2-3** and **Table 2-4** below.
- G-CSF and other hematopoietic growth factors may be used during the study in the management of acute toxicity such as febrile neutropenia when clinically indicated per ASCO Recommendations for Therapeutic Use of CSF (26) or at the discretion of the investigator; however, they may not be substituted for a required dose reduction.
- Blood transfusions and therapy with IV or subcutaneous erythropoietin-stimulating agents (epoetin alpha, darbepoetin alpha) are allowed per institution guidelines but may not be used as substitute for a required dose reduction (see also **Table 2-8**).
- Platelet transfusion may be used during the study in the management of acute toxicity such as hemorrhage or bleeding events, however they may not be used as substitute for a required dose reduction.

Table 2-3: Dose adjustments in response to neutrophil and platelet nadir ^a counts of the previous cycle

Absolute neutrophil nadir count of the previous cycle (/mm³)		Platelet nadir count of the previous cycle (/mm³)	Anetumab ravtansine dose adjustment ^b
≥ 500 or < 500 for < 7 days	and	≥ 25,000	No change
< 500 for ≥ 7 days	and/	< 25,000 regardless of the presence of active bleeding (or ≥ 25,000 with clinically significant bleeding, i.e. bleeding requiring platelet transfusion)	Decrease 1 dose level ^b
Febrile neutropenia ^c	and/	< 25,000 regardless of the presence of active bleeding (or ≥ 25,000 with clinically significant bleeding, i.e. bleeding requiring platelet transfusion)	Decrease 1 dose level ^b

ANC = Absolute neutrophil count; C = Cycle; CBC = Complete blood count; D = Day; Q3W = Every 3 weeks

- a Site visits and blood test for CBC (and biochemistry) on D8 and D15 will be performed on C1, C2 and C3 only. From Cycle 4 onwards, visits and procedures on D8 and D15 are no longer required.
- b Dose reduction by 1 dose level translates to a change from 6.5 mg/kg Q3W to 5.5 mg/kg Q3W, or from 5.5 mg/kg Q3W to 4.5 mg/kg Q3W. Not more than 2 dose reductions from the starting dose level are permitted.

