After dose reduction, there could be no intra-patient dose escalation irrespective of the type of TEAE that has led to dose reduction in this patient.

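### The Grade 3 corneal cell of Table 2-6 conflicts with the rest of the protocol: it uses a -3 dose level that does not exist, continues dosing through an unresolved event, and re-starts after a hold that no corneal rule orders; Section 7.3.2.4 adds a different re-start grade

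*Combined protocol and SAP*

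**What the plan says.** Section 7.3.2.2 lists Bayer Grade 3 or higher corneal toxicity among the events that require dose or infusion modification. The instruction for Grade 3 is one cell of Table 2-6 in Section 7.3.2.3, and it has three items:

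- **Item 1:** go down to level -1, "or -2 dose level if event does not resolve to Grade ≤ 2 at the -1 dose level within 3 weeks".
- **Item 2:** "Re-start at the original dose level if the first Grade 3 event resolves to Grade ≤ 2 within 3 weeks and does not recur".
- **Item 3:** "If not resolved within 3 weeks continue at reduced -2 dose level (or -3 dose level").

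Grade 3 in that table is a corneal ulcer not at risk of acute rupture, or a central stromal opacity. Anything worse is Grade 4 and ends treatment.

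Other parts of the protocol bear on the same patient:

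- **Table 2-2** defines 6.5, 5.5 and 4.5 mg/kg, and the footnote to Table 2-3 adds: "Not more than 2 dose reductions from the starting dose level are permitted".
- **Figure 2-1** (Section 6.3.2) lists as a reason for withdrawal: "TEAE requiring dose reduction when already at the 4.5 mg/kg Q3W dose level (minimum dose").
- **Section 7.3.2.2**, at its end, says that after a reduction "there could be no intra-patient dose escalation irrespective of the type of TEAE that has led to dose reduction".
- **Table 2-5** handles other Grade 3 non-hematologic events with "Delay/Interruption until Grade ≤ 2", but the text that applies it covers toxicities "other than corneal toxicity and infusion reaction/hypersensitivity events, and the continuation of treatment is appropriate".
- **The lead-in to Table 2-6** names two actions for corneal changes, reduction and permanent discontinuation. Section 7.3.2 also counts temporary interruption as a form of dose modification in general.
- **Section 7.3.2.4** allows a re-start once the event is below Grade 2 within six weeks of the last dose.

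**The concern.** Section 9.5.1.6 makes corneal disorders the adverse events of special interest, so this is the safety rule that most needs to be unambiguous. As written, three sites faced with the same Grade 3 eye finding could dose on at a lower level, hold and re-start at the original dose, or withdraw the patient, and each could cite the protocol.

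The written rule is also weaker than the one for ordinary Grade 3 non-hematologic toxicity, which is delayed until it improves. That is hard to square with Section 3.1, which reports that corneal toxicity in the Phase I expansion cohort always led to a long break in treatment as well as a lower dose. The break is the step missing from the corneal instruction.

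**Working it through.** The protocol gives no figure to reproduce here. The check sets the rules side by side; a small dose calculation then shows what the choice of reading does.

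**1. The dose ladder.** From 6.5 to 5.5 to 4.5 mg/kg is two reductions, which is the permitted maximum. A -3 level would be a third. If the 1.0 mg/kg step were extended (an assumption), it would be 3.5 mg/kg, below the stated minimum. For a patient already at 4.5 mg/kg, item 3 can be read as continue and Figure 2-1 says withdraw.

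**2. Dosing while unresolved.** Three weeks at level -1 is one 21-day cycle. If the event is still above Grade 2 at that point, items 1 and 3 call for the next infusion at level -2 while the Grade 3 finding is present. Each infusion also restarts the Figure 2-1 clock, which runs for six weeks from the last dose.

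**3. The two readings of item 2.**

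| Reading of the re-start | Obstacle |
|---|---|
| It ends a hold | No corneal rule orders a hold, and item 1 still has the patient on level -1 during those three weeks |
| It reverses the item 1 reduction | Section 7.3.2.2 bars re-escalation whatever the type of event |

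**4. The re-start grade.** Take a patient whose event has improved to Grade 2. Tables 2-5 and 2-6 allow a re-start; Section 7.3.2.4 does not. Figure 2-1 and footnote b of Table 2-5 also stop treatment if Grade 1 or lower is not reached within six weeks. These are stop rules, so they can stand beside either re-start grade, except at week 6, where a patient still at Grade 2 meets both.

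**5. Illustration per event.** Assumptions: infusions planned on days 0, 21 and 42; Grade 3 found on day 14, which the 7-day window for eye exams in Section 9.2.3.2 allows; dose counted to day 42. Planned dose: 3 × 6.5 = 19.5 mg/kg.

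| Course | Dose to day 42, mg/kg | Share of plan |
|---|---|---|
| Improves to Grade 2: item 1, then back to full dose (breaks the ban) | 6.5 + 5.5 + 6.5 = 18.5 | 95% |
| Improves to Grade 2: item 1, ban respected | 6.5 + 5.5 + 5.5 = 17.5 | 90% |
| Hold, improved by day 21, original dose | 6.5 + 6.5 + 6.5 = 19.5 | 100% |
| Hold, improved after day 21 and by day 35, original dose | 6.5 + 6.5 = 13.0 | 67% |
| Hold under Section 7.3.2.4, Grade 2 persisting to day 42 | 6.5 | 33% |
| Unresolved to day 42: items 1 and 3, dosing on | 6.5 + 5.5 + 4.5 = 16.5 | 85% |
| Unresolved to day 42: hold, then withdrawal | 6.5 | 33% |

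In the 13.0 mg/kg row the third infusion is postponed past day 42 and not necessarily lost.

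**The case against.** The strongest defence is that dosing on at a lower level is a deliberate choice. It is paired with intensive eye treatment and close ophthalmologic follow-up, and the more dangerous ulcers are Grade 4 and end treatment. Section 7.3.2 counts temporary interruption as a dose modification, and investigators may stop dosing that would harm the patient (Figure 2-1) or modify it for any clinically significant risk (Section 7.3.2.2). A reader might therefore infer from the point above that sites are forbidden to hold. The documents do not support that: a hold is permitted but not ordered.

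This explains item 1 in part, but it neither creates a -3 level nor reconciles item 2 with the re-escalation ban. One could say that Table 2-6, as the specific rule, overrides the general ones, but nothing in Section 7.3.2 says so, and the ban is worded to cover every type of event. The Table 2-6 pages carry an older version header, yet they sit in the body of Version 4.0 as its corneal dosing rule.

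Four stronger inferences fail:

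- **That a hold always costs exposure.** If the event improves by day 21 and the original dose is resumed, a hold gives 19.5 mg/kg, which is 2.0 more than the 17.5 under item 1 with the ban.
- **That Section 7.3.2.4 is simply the wrong one.** Its threshold equals the Grade 1 level in the stop rules, so tightening the tables is as open to the sponsor as loosening that section.
- **That 12 of 32 in Section 3.1 estimates how often Grade 3 occurs.** Those events were attributed to microcysts or deposits, which are Grade 2 morphology in Table 2-6.
- **That the footnote basing decisions on morphology leaves vision loss without a rule.** Section 7.3.2.3 already allows modification for Grade 2 or lower corneal toxicity with impaired vision.

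**Conclusion.** The point holds as a conflict between operative rules. The -3 level contradicts Table 2-2, the two-reduction cap and Figure 2-1. Continued dosing during an unresolved Grade 3 event is at odds with Table 2-5 and with the Phase I experience in Section 3.1. Item 2 has no reading that fits the other rules, and the re-start grades differ. These conclusions need only the text.

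The size is per event. Under the day-14 scenario, the dose to day 42 runs from 6.5 to 19.5 mg/kg depending on the reading and the time to improvement; for an unresolved event the contrast is 16.5 against 6.5 mg/kg. These are illustrations, not expected effects, because the documents give no Grade 3 frequency and no time to resolution. A reader might infer that the response-rate test is compromised. The Simon boundaries and error rates do not depend on this rule, so the point concerns eye safety and consistent conduct across sites. It should be corrected.

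**What to change.** 1. In the Grade 3 cell of Table 2-6, delete the bracket that names level -3 and replace the instructions with: *Hold dosing until Grade ≤ 2, then re-start one dose level lower. If a further reduction is needed at 4.5 mg/kg, or the Figure 2-1 six-week limits are exceeded, discontinue.*
2. If the sponsor wants to keep item 2, state that re-start at the original level applies only to a first event that resolves during a hold within 3 weeks, before any reduced dose is given. Whether to do so is a clinical choice, and the Phase I experience in Section 3.1 argues for caution.
3. Add temporary interruption to the bracket in the Section 7.3.2.3 lead-in.
4. Use one re-start grade in Section 7.3.2.4 and Tables 2-5 and 2-6. Which grade is the sponsor's decision. If it is Grade 1 or lower, the hold in step 1 changes with it. If it is Grade 2 or lower, say what happens to a patient still at Grade 2 at week 6, when the Figure 2-1 stop applies.

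The footnote on visual acuity can stay as it is.

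Cost: a text amendment. A Grade 3 event may delay an infusion, and a hold may need an unscheduled eye exam, because the mandatory ones are tied to infusions. The effect on exposure depends on time to resolution. In the day-14 scenario, with the re-start one level lower:

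- **Improved by day 21:** 6.5 + 5.5 + 5.5 = 17.5 mg/kg, the same as item 1 with the ban respected.
- **Improved later, re-started by day 42:** 6.5 + 5.5 = 12.0 mg/kg to day 42, which is 5.5 less than that course, in part only postponed.
- **Not improved by day 42:** 6.5 mg/kg and discontinuation, against 16.5 when dosing on, a difference of 10.0.
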